11.2 Determination of Sample Size

Based on a review of studies on pain during a PIC insertion (Baxter et al., 2009; Dutt-Gupta et al., 2007; Fossum et al., 2016; Fry et al., 2001; Hartstein et al., 2008; Kim et al., 2012; Marco et al., 2007; Ott et al., 2007), 2012; Soysal et al., 2005; Speirs et al., 2001; Witting et al., 2016), the mean pain intensity is estimated at 34 mm by the Visual Analog Scale (with a possible intensity between 0 and 100 mm), with a standard deviation estimated at 24 mm. To detect the smallest decrease in clinically significant pain intensity of 13 mm (Todd et al., 1996) due to the intervention, a sample of 110 patients, or 55 patients per arm, is required, with a power set at 80% and alpha set at 5%. Taking into account missing values or refusal to participate after randomization estimated at 10% of patients, 60 patients will be randomized per arm. A total of at least 240 patients will therefore be recruited for the two phases, i.e. the four arms, of the study.

11.3 Statistical criteria of termination of trial

Non-applicable.

11.4 Planned Analyses

Descriptive data will be presented by mean and standard deviation, median and interquartile space or proportions for Gaussian, non-Gaussian and categorical continuous variables. The comparison between randomized groups will be done by Student t-test or Wilcoxon rank sum test for continuous variables, and by Chi2 or Fisher for categorical variables, as appropriate.

The analyses will be performed using Stata software version 14 (StataCorp, TX, USA). The analysis will be performed by the principal investigator. To ensure that he is not aware of the assignment of patients to the intervention or control group, co-investigators will delete the patient number corresponding to that of the randomization list before the database is transmitted. Thus, the analysis of the data will be done blind. It is therefore a triple-blind study.

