6.2 Methods of minimising bias

6.2.1 Randomisation

In the first phase of the double-blind study, a randomization method by permutation of blocks of 4 and 6 patients will be used. The principal investigator, who will not collect data, will create the randomization list and hold the randomization seed.

In the second phase, only patients will be blind, but the assignment of one of the two messages will also be done by block permutation of 4 and 6.

In both phases of the study, randomization will occur immediately after verbal consent, before the intervention or control message is delivered.

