6.2.2 Blinding procedures

During the first phase, the allocation of the arm « control message » or of the arm « intervention message » will be determined by a code written on a card inside a sealed and opaque envelope, prepared by the principal investigator. This code will indicate the number, between 1 and 130, of the audio track to be played to the patient and will be recorded in the CRF. In the second phase, the note « control message » or « intervention message » written on the card will indicate to the caregivers the message to be delivered and will be reported in the CRF. Envelopes will be numbered consecutively, and the co-investigators will open them consecutively, noting each time the opening date. The principal investigator will regularly verify that the order of opening is respected by checking the number of envelopes opened and the opening dates against the number of patients included in the study.

The first phase of the study will be carried out in double blind (patient, caregiver, co-investigator) thanks to the coding of audio recordings. In the second phase, only patients will be blinded to the tested component.

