6.2.3 Other methods of minimising bias

Based in particular on the limitations identified from the studies included in the 2015 systematic review (Mistiaen et al., 2016), the following measures were taken to minimize as much as possible the bias that could result from this study:

- Integrity of the intervention: most of the studies included in the systematic review had not verified the accuracy of their intervention. In both phases of our study, caregiver behaviour will be reported in the CRF according to Kaptchuck criteria. In the first phase of the study, caregivers will be instructed to act naturally with patients during the procedure, without referring to the ongoing study throughout the entire duration of the procedure or commenting early on the PIC placement. Any interactions will be reported in the CRF under the « Difficulty(-ies) encountered » category. In the second phase, the script as it has been verbalized by the caregivers will also be globally reported. The content of the message delivered by caregivers will be reported in writing to the CRF as key words/concepts, checked off once they have been stated. For key words/concepts that would not be included in the original script, but which would still be mentioned by caregivers, they will be reported specifically under the « Other(s) » category. We have also scheduled for each phase an information session for the emergency care staff on the progress of the study and the content of the messages at one of their monthly team meeting, which will then be the subject of a report sent to the entire team;
- Statistical considerations: most of the studies included in the systematic review had not calculated an *a priori* statistical power, and since many studies included a small number of patients (from 19 to 771 with an average of 110 patients per study), divided into several intervention arms, the probability was high that a real effect could not be detected. We calculated an *a priori* statistical power in our study and set a minimum number of participants at 240;
- Retention of baseline demographic data (sex, age) of patients who have revoked consent or who were excluded from the study to ensure that they are similar to patients included on these

two criteria;

- Intervention control not described: we plan to transcribe the texts of the messages intervention and control in the presentation of the results of the study;

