6.3 Unblinding Procedures (Code break)

Only the principal investigator will hold the coding key and it will only be revealed once all the data has been collected, entered into the database and statistically analyzed.

In case of an urgent situation, the allocation to one of the arms can be obtained from the principal investigator.

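### Section 11.4 calls the analysis blind and the study triple-blind, but the planned step does not mask the analyst and phase 2 is single-blind

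*Combined protocol and SAP*

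**What the plan says.** Section 11.4 names the principal investigator as the analyst. To keep this person unaware of allocation, "co-investigators will delete the patient number corresponding to that of the randomization list before the database is transmitted". It then concludes: "Thus, the analysis of the data will be done blind. It is therefore a triple-blind study". The statement is not limited to one phase.

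Other sections describe the same person's role in allocation:

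- Section 6.2.1, under phase 1: "The principal investigator, who will not collect data, will create the randomization list and hold the randomization seed".
- Section 6.2.2: the phase 1 arm "will be determined by a code written on a card inside a sealed and opaque envelope, prepared by the principal investigator". The principal investigator also checks the order and dates of envelope opening.
- Section 6.3: "Only the principal investigator will hold the coding key". The key is to be disclosed only after collection, entry and statistical analysis.

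The arm is recorded as follows:

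- Phase 1, section 6.2.2, as a CRF entry: "This code will indicate the number, between 1 and 130, of the audio track to be played to the patient and will be recorded".
- Phase 2, section 6.2.2: the card names the control or the intervention message, and this note "will indicate to the caregivers the message to be delivered and will be reported in the CRF".
- Phase 2, section 6.2.3: "The content of the message delivered by caregivers will be reported in writing to the CRF as key words/concepts".

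The synopsis (Study design) and sections 6.2.1, 6.2.2 and 6.2.3 all describe phase 2 as blind for the patient only.

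**The concern.** Deleting a number masks an analyst only if nothing else in the file reveals the arm and the analyst has no other route to it. Here the analyst holds the phase 1 key, and in phase 2 the arm is written down. The triple-blind label also conflicts with the protocol's own account of phase 2.

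What is at stake is mainly the accuracy of the report: repeating section 11.4 would claim a level of blinding that the design does not provide. A second matter is that some choices remain open at analysis. There is no criterion for a Gaussian distribution (11.4.2), clustering by caregiver is used only if needed (5.2, 9.2.1), and no threshold defines a fully delivered message (11.4.3). Those gaps need pre-specification in their own right. The point here is only that a reader could not assume they were settled without knowledge of the arm.

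**Working it through.** The check traces who can link a record to an arm. The only arithmetic is the number of patients covered.

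**Patients covered.** Section 11.2 gives 60 randomised per arm. Per phase: 60 × 2 = 120. Both phases: 120 × 2 = 240, which reproduces the plan's minimum total. Phase 2 is 120 / 240 = one half. The sample size, alpha and power are not affected by this point.

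**Phase 1.** Section 6.2.2 gives a track number as the recorded allocation, and track numbers do not form two groups until decoded. Section 11.4 does not say exactly which number is deleted, so there are two cases.

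1. The track number stays in the file. The comparison in section 11.4.2 then needs the key. Only the analyst holds it, and using it reveals the arm. Section 6.3 also places disclosure of the key after the analysis.
2. The track number is the deleted number. No recorded phase 1 variable is then left from which to form the groups.

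In neither case can the co-investigators supply a neutral A/B code, because they are blinded in phase 1 and do not hold the key. Section 6.1 lists the message delivered as a CRF variable. In phase 1 that can only be the coded track number, since an arm in words would break the co-investigators' own blind. If section 6.3 means disclosure to everyone else, the analyst may use the key during the analysis, and the analysis is then not blind.

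**Phase 2.** The arm can be read from two places.

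1. The message label is reported in words (6.2.2).
2. The script is recorded by checked key words (6.2.3), and the key elements differ by arm. Section 8.1.1 lists dissociation of the arm and a sense of control; section 8.1.2 lists the tourniquet, the sensation of the needle and lack of control.

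Three other sections suggest that this information enters the database. CRF data are double-entered (12.1.1). The monitor verifies the message received and checks its correct entry (12.3). The investigators have access to all study data except the caregiver coding key (12.5). The analysis restricted to fully delivered messages (11.4.3) also needs script information, and no derived completeness flag is planned.

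**Comparison within the plan.** Section 9.2.1 has the caregiver number recoded at data entry so that the analyst cannot identify caregivers. No equivalent step exists for the arm.

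**Label.** Section 11.4 says triple-blind for the study. The synopsis and sections 6.2.1 to 6.2.3 say single-blind for phase 2. These cannot both stand, and this conflict needs no inference about the transferred file.

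**The case against.** The strongest reply has four parts.

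- **One masking step is planned.** This is true. Deleting the patient number removes a direct link to the randomisation list. It does not remove the phase 1 track number (unless that is the number meant) or the phase 2 label.
- **The evidence on the analyst's file is incomplete.** This stands as a limit. The fields sent to the analyst are not listed, and the CRFs are not in the text. The list in section 12.3 is loose, since it includes patient names that section 12.2 keeps out of the database. Section 6.2.1 names the list-maker under phase 1 only, so a reader who infers that the principal investigator also makes the phase 2 list goes beyond the documents. The phase 2 argument rests on the recorded label instead.
- **The consequence is small.** This also stands. Pain is self-rated by blinded patients (9.2.1), entry is double (12.1.1) and the completed database cannot be modified (12.2).
- **The correct blinding is stated elsewhere.** It is, in several places. That limits the harm of the label but does not make section 11.4 right.

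A reader might also see a discrepancy in 130 track numbers against 120 planned phase 1 patients. There is none: the recruitment total is a minimum, and spare tracks are unremarkable.

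**Conclusion.** Section 11.4 is wrong as written on both counts. The triple-blind label contradicts the protocol's own description of phase 2, which is half of the planned minimum of 240. The blind-analysis claim is not supported in either phase: in phase 1 the analyst alone holds the key needed to form the groups, and in phase 2 the arm is recorded in words with no recoding planned.

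The label conflict and the key-holder conflict follow directly from the text. What the analyst would see in the phase 2 file is an inference, though sections 6.1, 12.1.1, 12.3 and 12.5 point the same way.

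A reader might infer that the results will be biased, or that the principal investigator would look up allocations. The documents do not support that. They show that the procedure does not secure unawareness, not that it would be abused. Any bias would act through analytic choices, is likely to be small and cannot be quantified from the documents. Nor does the point weaken the planned blinding of patients in both phases, or of caregivers and co-investigators in phase 1.

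**What to change.** **Required (wording only, no cost).** In section 11.4 delete the triple-blind label and the claim of a blind analysis. Describe phase 1 as double-blind (patient, caregiver, co-investigator) and phase 2 as single-blind (patient). State that the analyst is not masked to arm.

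**Optional, only if the sponsor wants to keep a blind analysis and a person is available.**

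- Someone other than the analyst creates and holds the list and key, prepares and checks the envelopes, and supplies a neutral A/B code at database lock.
- The analyst does not receive the track number, the message label, the itemised script fields, or any date or sequence number that can be matched to the envelopes.
- A yes/no completeness flag is supplied for the analysis in 11.4.3.
- Sections 6.2.1, 6.2.2, 6.3 and 11.4 are reconciled with the new roles. This includes who answers an urgent code-break request, which section 6.3 now assigns to the principal investigator.

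The option costs one independent person's time over the whole allocation process, a recoding step at lock and edits to four sections. The biostatistical consultation in section 1.3 is a possible candidate, but the protocol gives it only a support role and shows no agreement to do this. Neither version adds patients or study procedures.

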11.4.1 Datasets to be analysed, analysis populations

A first analysis will be made by « intention to treat ». Subsequently, a second « per protocol » analysis may address any differences between patients who received a complete or incomplete message in the second phase of the study.

11.4.2 Primary Analysis

The primary analysis will compare the pain intensity and unpleasantness after the PIC insertion as measured by VAS. The VAS will be compared by Student t-test if the distribution is Gaussian or by Wilcoxon rank sum test if not. The analysis will be conducted according to the « intention to treat » principle, which will include all randomized patients.

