5.2 Secondary Outcomes

The secondary outcomes of this study will be patients' assessment of their anxiety at PIC insertion and caregivers' assessment of patients' pain intensity and unpleasantness and anxiety at PIC insertion (Singer et al., 1999).

Other co-variables will be reported in the CRF to the extent that they may influence primary or secondary outcomes:

- The intensity and unpleasantness of pain and anxiety level assessed by patients prior to the CIP;
- Reason for consultation (internal medicine, traumatology or surgery);
- Any painkillers already given/ongoing in the ED (what, when, administered by whom);
- The caregivers' behaviour during the procedure;
- The patients' algic behaviour during the procedure;
- Procedure' characteristics (location, caliber, number of attempts, difficulties and complications encountered);
- Report of a possible fear of needles (« Are you generally afraid of needles? »);
- Report of a possible chronic pain (« Do you suffer from chronic pain, i.e. that has lasted for more than three months? ») and chronic painkillers consumption.

The sex, age, origin and educational background of patients, as well as the sex and age of caregivers, will also be reported to the extent that they may influence caregivers' assessment of patients' pain intensity and unpleasantness and anxiety level (Li et al., 2001; Nevin, 1996; Singer et al., 1999).

Finally, in the second phase, a unique coded number related to the study (study number) will be assigned to each caregiver and reported in the CRF when the PIC is inserted. If needed, it will allow the analysis of data by grouping patients by caregiver.

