9.2 Assessments of outcomes

9.2.1 Assessment of primary and secondary outcomes

The primary outcomes, the intensity and unpleasantness (emotional component) of pain experienced by patients during the PIC insertion, will be measured using a Visual Analog Scale (VAS) (Lang et al., 2014; Pagé et al., 2012). Patients' anxiety, as a secondary outcome, will also be measured by VAS. These three measurements will be performed by using three rulers after the PIC is inserted. These three rulers, with three different color codes to distinguish them, will be presented to the patients who will move the three sliders on a line going from one extreme to the other (No pain / Worst pain imaginable; Experience not at all unpleasant / Most unpleasant experience possible; Not at all anxious / Extremely anxious) and corresponding, on their other side, to a value between 0 and 100 mm on a 100 mm long line. This numerical value measured in millimetres will be reported in the CRF by the co-investigators. Patients will be asked to rate their overall feelings after the PIC insertion regarding these three aspects. The co-investigators will ensure that the caregivers do not become aware of the patients' responses.

As for caregivers' assessment of patients' pain intensity and unpleasantness and anxiety, these secondary outcomes will also be measured using the three VAS, this time in paper format and reported in the CRF after the PIC insertion. Caregivers will mark their estimation by tracing a line on each of the three VAS once they have completed their procedure, making sure that patients do not read their answers. The co-investigators will then measure the distance between the 0 extreme and the line traced by the caregivers in millimetres and report this numerical value in the CRF.

Before the PIC insertion, patients will assess the intensity and unpleasantness of any pre-existing pain and their basal anxiety level with these same three VAS. This will give a baseline value for these three measures. These values will be reported in the CRF before the PIC is inserted, along with the reason for consultation (internal medicine, traumatology or surgery) and any painkillers already given/ongoing in the ED.

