11.1 Hypothesis

First null hypothesis: The recorded intervention message has an effect comparable to that of the recorded control message on the painful feeling induced by the insertion of a PIC.

First alternative hypothesis: The recorded intervention message reduces the intensity and unpleasantness of the pain induced by a PIC insertion of at least 13 mm from the recorded control message.

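### An undefined normality check picks the primary test, no between-arm estimate or confidence interval is planned for a 13 mm hypothesis, and baseline VAS is left out of the outcome analysis

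*Combined protocol and SAP*

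**What the plan says.** **Test.** Section 11.4.2 compares post-insertion pain intensity and unpleasantness between arms: "The VAS will be compared by Student t-test if the distribution is Gaussian or by Wilcoxon rank sum test if not". Section 11.4.3 repeats the rule for patients who received the full message, for anxiety and for the caregivers' ratings. The synopsis and Section 11.4 add only that the choice is made as appropriate. No normality test, threshold or plot is named. Nor is it said whether each arm, the pooled scores or the residuals are checked.

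**Target.** Section 11.1 states as the alternative that the positive recording "reduces the intensity and unpleasantness of the pain induced by a PIC insertion of at least 13 mm from the recorded control message". Section 11.2 sizes the trial on the same quantity: "To detect the smallest decrease in clinically significant pain intensity of 13 mm", with mean 34 mm and SD 24 mm.

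**Reporting.** Section 11.4 says "Descriptive data will be presented by mean and standard deviation, median and interquartile space or proportions for Gaussian, non-Gaussian" and categorical variables. These are summaries of each group. Section 11 does not mention a between-arm difference, a shift or a CI.

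**Baseline.** Under Section 9.2.1, before insertion, "patients will assess the intensity and unpleasantness of any pre-existing pain and their basal anxiety level with these same three VAS". Section 5.2 puts these ratings first in a list introduced by "Other co-variables will be reported in the CRF to the extent that they may influence primary or secondary outcomes". Sections 11.4.2 and 11.4.3 compare post-insertion scores only.

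**Masking.** Section 11.4 says "Thus, the analysis of the data will be done blind". Section 6.3 says of the coding key that "it will only be revealed once all the data has been collected, entered into the database and statistically analyzed".

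**The concern.** The question in Section 11.1 is about millimetres on a 0–100 scale. The plan may answer it with a rank test that gives no millimetre result, and which answer is given depends on a check that two competent analysts could carry out differently.

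Three things are at stake:
- whether the primary result is a comparison of means or of ranks, and in some trials whether it is significant;
- whether readers get an interval to set against 13 mm;
- whether a covariate already collected is used to sharpen that interval. This is the smallest of the three.

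**Working it through.** **1. The plan's own figure.** Inputs from Section 11.2: difference 13 mm, SD 24 mm, power 80%, alpha 5%. Sidedness is not stated.
- Normal formula, two-sided: n = 2 × [24 × (1.960 + 0.842) / 13]² = 53.5, so 54 per arm.
- Two-sample t-test (noncentral t): 54.5, so **55 per arm, as stated**. Power at 55 is 80.4%.
- A one-sided normal formula gives 43 and does not match.

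The design therefore assumes a two-sided comparison of means.

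**2. Is the rank-sum branch likely?** With mean 34 and SD 24, zero lies 34/24 = 1.42 SD below the mean, so a normal model puts 7.8% of scores below 0. At mean 34 − 13 = 21 with the same SD it puts 19.1% there. Scores are therefore likely to be skewed.

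**3. Does the choice matter?** Simulation, 55 per arm. Assumed shapes: beta, or normal censored at 0 and 100. Control mean 34, SD 24; intervention mean 21, with SD 24 (from Section 11.2) or 18 (assumed).
- The t-test and rank-sum test disagree on significance in 14.1% and 5.3% of trials (beta, SD 24 and 18) and in 7.8% and 6.8% (censored). With no effect they disagree in 1.4–2.0%.
- Type I error: t-test 5.0–5.2%, rank-sum 4.3–5.2%, Shapiro-Wilk followed by the chosen test 4.5–5.2%.
- A Shapiro-Wilk check in either arm sends 88–100% of trials to the rank-sum branch. A skewness-kurtosis check sends 32–99%. Choosing between these two checks changes the significance verdict in 0–0.8% of trials (beta) or 0.5–2.9% (censored). Adding a third reading, absolute skewness above 1, raises this to about 1–7%, but that cut-off is an illustration and is not in the documents.

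**4. What a CI adds.** At 55 per arm the standard error is 24 × √(2/55) = 4.58 mm. The half-width is 1.982 × 4.58 = 9.07 mm. An observed difference of about 9.1 mm is therefore already significant. For the whole CI to lie beyond 13 mm, the observed difference must exceed 13 + 9.07 = 22.1 mm. A p-value against zero does not address a reduction of at least 13 mm.

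**5. Baseline adjustment.** The residual SD is 24 × √(1 − r²), where r is the correlation between baseline and post-insertion VAS. The documents do not give r.

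| Assumed r | Residual SD (mm) | Power at 55 per arm | CI half-width (mm) |
|---|---|---|---|
| 0 (unadjusted) | 24.0 | 80.4% | 9.07 |
| 0.1 | 23.9 | 80.8% | 9.03 |
| 0.2 | 23.5 | 81.9% | 8.89 |
| 0.3 | 22.9 | 83.9% | 8.65 |
| 0.5 | 20.8 | 90.2% | 7.86 |

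**6. Missing baselines.** Suppose 5% are missing (assumed) and those patients are dropped, leaving 55 × 0.95 = 52.25 per arm. Half-widths become 9.27, 9.13, 8.89 and 8.07 mm for r = 0.1, 0.2, 0.3 and 0.5. That is worse than no adjustment when r < √0.05 = 0.22. Filling in the pooled mean gives 9.03, 8.90, 8.68 and 7.92 mm and keeps every patient who has an outcome.

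**7. Caregivers in phase 2.** With 15 caregivers, within-caregiver correlation 0.05, a constant effect and very unequal workloads (all assumed), clustered standard errors reject in 6.2–8.2% of null trials, against 4.8–5.6% for ordinary robust ones. If the effect varies between caregivers with SD 10 mm (assumed), ordinary robust errors reject in 6–10% with 15–30 caregivers, and clustered ones in 8.0–9.9% when workloads are very unequal. Neither choice is safe without a small-cluster correction.

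**The case against.** The strongest defence is that a t-test with a rank-sum fallback is an ordinary plan, that it keeps its type I error, and that in the Gaussian branch the reader can work out the difference and CI from the planned means and SDs. All of that stands. It leaves the criterion undefined and the rank-sum branch without a millimetre result.

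A second defence is power. Section 11.2 gives one SD, 24 mm. With that SD in both arms, the rank-sum test does better under skewed shapes: 93% against about 79–88% for the adjusted mean difference (beta, r 0.1–0.5), and 88% against 80% for the unadjusted t-test (censored). This also stands, with two limits. The beta shape is extreme, with 37% of intervention patients below 5 mm. The order reverses if the intervention SD is lower: 85% for rank-sum against 89–94% at an assumed SD of 18.

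Third, masked analysis limits picking a test for its result. That is a fair answer for phase 1. It is weaker in phase 2, because Section 6.2.2 has the named message entered in the CRF, so deleting the patient number may not hide the arm.

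A reader might also infer that baseline VAS is used nowhere. The documents do not support that: the general sentence on continuous variables in Section 11.4 could cover a baseline table or comparison. What is missing is its use in the outcome analysis. Nor do the documents support reading the fallback rule as a false-positive problem or the sample size as wrong.

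**Conclusion.** The point holds as a gap in specification and estimation, worth fixing but not a validity error. The choice of primary test is undefined, and no millimetre effect or CI is planned for a trial designed around 13 mm. Baseline VAS is also left out of the outcome analysis.

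The t-test and rank-sum test would reach different significance verdicts in roughly 5–14% of trials with a 13 mm effect and 1–2% with none. These figures rest on assumed score shapes. Disagreement between the two standard normality checks is smaller, at most about 3%, so the lack of an estimate matters more than the wording of the check.

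The gain from baseline adjustment is uncertain. It is negligible below r of about 0.2, and r may well be low because the baseline scale rates pre-existing pain, not insertion pain.

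The comparison of audio with caregiver delivery is a separate matter and is not judged here.

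**What to change.** In Sections 11.4.2 and 11.4.3, replace the rule with the following:
- For each patient-rated VAS, in each phase, the result is the mean difference in mm with 95% CI from a linear regression of post-insertion VAS on arm and the matching baseline VAS, with robust standard errors, whatever the distribution.
- The Wilcoxon rank-sum test, with a Hodges-Lehmann shift and 95% CI, is a sensitivity analysis.
- A CI that excludes 0 in the direction of less pain shows a reduction. A reduction of at least 13 mm is claimed only if the whole CI lies beyond 13 mm.
- A missing baseline VAS is filled in with the mean of that scale, both arms pooled. Section 11.5 currently rules out imputation for anything but the primary endpoint, so the exception must be noted there.
- Caregiver clustering in phase 2 is a sensitivity analysis with a small-cluster correction. This fits Section 9.2.1, which foresees such an analysis if necessary, and uses the caregiver number already recorded.
- Caregiver-rated VAS have no baseline; report the unadjusted mean difference with 95% CI.

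In Sections 6.1 and 6.2.1, state that baseline VAS is recorded before the envelope is opened, at least in phase 2, where the card names the arm. The current text places randomisation first. If that order is not adopted, make the unadjusted mean difference with 95% CI primary in phase 2.

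**Cost.** No new data are needed. The estimate and CI take SAP wording and a few lines of Stata. Adjustment also needs the Section 11.5 exception and the change in bedside order. The price is the possible loss of power against the rank-sum test under strong skew with equal SDs. Under Section 2.10 the change may be a substantial amendment, needing ethics committee approval and notice to the registries. It must be fixed before unblinding.
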